### 3. STUDY DESIGN

---

[figure not shown]
In this study, we will refine and feasibility-test our mindful self-compassion program and an attention control program with a focus on adolescents who are experiencing subsyndromal depression. Subsyndromal to mild depression is defined as a score of at least 6 and 10 on the Quick Inventory of Depressive Symptoms (QIDS). The intervention program, called “Making Friends with Yourself” (MFY), implements mindfulness and self-compassion training. The control condition is a healthy lifestyle program for high-school aged adolescents. The control condition was developed by our team as an attention control group for our pilot adolescent mindfulness program and will be adapted for comparison with the MFY intervention. The 8-week programs will be piloted with a total of 80 adolescents. After completion of the 8-week program, the teens will participate in a post-group meeting to give feedback about program contents. Feedback will take place in the form of a focus group. Following the 8-week program, adolescents will be invited to participate in 6 monthly continuation sessions, designed to strengthen understanding of the topics presented in the 8-week course. Measures of depression, resilience, brooding, shame, mindfulness, and self-compassion will be obtained before the 8-week program, halfway through the program, after the 8-week program (intervention phase), and 3 and 36 weeks after program completion (continuation phase). Feedback from program participants will inform modifications and refinement of both programs.

Our primary goal is to examine the feasibility of implementing the program. After feasibility, the primary outcome to be explored will be the occurrence of incident major depressive disorder (MDD) with a secondary outcome to be explored being the trajectory of depressive symptoms over time (measured at baseline, program end and at 3 and 36 weeks post program) using the Short Mood and Feelings Questionnaire (SMFQ) administered to both the adolescent and a parent. Studies indicate high predictive validity in adolescent self-report of depression. The study psychologist will contact parents of teens with incident major depression, captured by the SMFQ at any of the scheduled time-points during the study, for referral to appropriate mental health care.

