### 8.3: Early discontinuation

Participants will continue to be followed, with their permission, for another 6 weeks if study interventions are discontinued for reasons other than the normal end of the study. Permission will be sought for questionnaire completion at stopping.

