### 8.4: Normal end to the study

At the end of the 8-week intervention, subjects completing that part of the study will be followed for another 36 weeks with encouragement to maintain their assigned home practice. Questionnaires will be completed at 22 weeks post-intervention (Visit 13) and 36 weeks post intervention (Visit 16).

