### 9.4.2: Individual stopping rules

If a participant scores above 12 on the combined parent and child SMFQ at any point in the study, s/he will be referred to the study psychologist ([name]) within 24 hours. The study psychologist will then contact the parent of the teen (within 24 hours) to inform the parent of the depression status of the teen. [name] will make an evaluation to determine if s/he can continue in the study and will refer the family for appropriate psychological care.

We have added a safety depression screening measure, the PROMIS pediatric depression scale, which will be administered weekly via REDCap. The Assessment Center at NIH provides a scoring algorithm with REDCap software, enabling use of the measure for safety monitoring. The Project Manager or trained designee will monitor these measures weekly and will alert the team (including the Study Psychologist) to sharp increases in depressive symptoms and depressive symptoms meeting criteria for major depression. If the Study Psychologist confirms the development of major depression, the adolescent will be withdrawn from the study and referred for further care.

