### 9.4.3: Additional Reasons for Withdrawal of a Participant

Additional reasons a participant may withdraw from the study include:

- The adolescent wishes to withdraw from the study;
- Loss of study eligibility (development of major depression);
- Intervening illness or injury making participation difficult;
- The adolescent develops any condition that, in the opinion of the study psychologist, would make continued participation unsafe.

In the unlikely event that a participant is unable to participate in a group setting, s/he may be withdrawn from the study.

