## 9.5: Outcomes

Our primary goal is to develop a depression-prevention program based on mindfulness and self-compassion and to establish the feasibility of its implementation as compared with an active attention-control comparator. Hence, the establishment of quality assurance processes and complete data documentation assume even greater importance than data analysis. Data of multiple types from multiple sources will be captured. For questionnaire assessments, secure internet-based data collection instruments will be used, accessible by internet-capable device.

Quality assurance of these measures will include review of study instruments for range and consistency checks, and descriptive analyses to assess distributions of study variables. Quality assurance of qualitative measures include 1) maintaining a spreadsheet to log scheduled, completed, transcribed, and analyzed focus groups and interviews; 2) establishing a transcription template to ensure data is uniform in appearance; 3) arranging for secure storage of recordings and transcripts on REDCap; 4) review of consistency of styles across interviewers; and 5) review of recordings to assess accuracy of transcriptions.

All statistical analyses will utilize all adolescents who were randomized to one of the intervention arms and who attended at least one class. Individuals who were unable to attend a class are excluded. Complete case analyses are planned (without imputations).

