### 9.5.2: Secondary Outcomes

For the secondary outcome, assuming feasibility is established, change in the Short Mood and Feelings Questionnaire (child and parent versions) will be examined in a linear regression in each condition, to test for any effect of either program. Then we will examine the change in depression scores through an

ANCOVA model controlling for baseline depression score and cohort to control for group specific effects. Subsequently, an exploratory analysis will examine the trajectory of changes over time by program arm, using graphical representations of outcomes at each time point by subject, cohort, and program arm as well as a longitudinal random effects model.

Hence, a within-group model would include terms for the follow-up depression score, the overall intercept, the cohort effect, the time effect, and a cohort\*time interaction—to allow the trajectory to vary by cohort—as well as random effects for individual subjects and subjects nested within cohorts. Between program arms, we would add terms for the program arm and its interaction with time.

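### SMFQ change at 22 or 36 weeks may omit teens withdrawn earlier for confirmed major depression, so within-arm improvement can look too good

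*Combined protocol and SAP*

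**What the plan says.** **Withdrawal.** Section 9.4.2 states: "If the Study Psychologist confirms the development of major depression, the adolescent will be withdrawn from the study and referred for further care". DSMP 7.3 repeats the sentence, and section 9.4.3 lists "Loss of study eligibility (development of major depression" among the reasons for leaving. An SMFQ alert alone leads only to an evaluation by the study psychologist; withdrawal follows confirmation.

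**After stopping.** Section 8.3 provides: "Participants will continue to be followed, with their permission, for another 6 weeks if study interventions are discontinued". It adds: "Permission will be sought for questionnaire completion at stopping". It does not name the instruments used in those 6 weeks.

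**Outcome and visits.** Section 3 describes the secondary outcome as "the trajectory of depressive symptoms over time (measured at baseline, program end and at 3 and 36 weeks post program". Section 8.4 sets the late visits: "Questionnaires will be completed at 22 weeks post-intervention (Visit 13) and 36 weeks post intervention (Visit 16".

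**Analysis.** Section 9.5.2 says that "change in the Short Mood and Feelings Questionnaire (child and parent versions) will be examined in a linear regression in each condition", followed by an ANCOVA and a longitudinal random effects model. Section 9.6.1 adds paired t-tests within each arm. Neither section names the visit at which change is taken. For all of these, section 9.5 says: "Complete case analyses are planned (without imputations".

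**The concern.** The SMFQ measures depressive symptoms. Under these rules a late score can be missing because the teen became depressed, so the teens left in a complete-case analysis are partly selected on the outcome. No section keeps a withdrawn teen on the 22- or 36-week SMFQ, and none says how a stopping score would enter the change analyses.

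Two results could mislead. Within-arm change, which the paired t-tests use to look for an effect of either program, would look too favourable in both arms. The between-arm difference would be too small if MFY prevents depression, because control would then lose more of its worst-off teens. Section 1.2 says these analyses inform the planning of the powered trial, so a distorted late estimate would carry into that plan.

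**Working it through.** **Inputs from the documents.** 80 teens, equal allocation, so 40 per arm; hazard ratio 0.52, which 9.2.1 calls detectable; SMFQ difference 4 with SD 6 (DSMP 7.2); more than 30% incident depression if untreated (9.2.1).

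**Assumptions.** Constant hazard over 44 weeks (8 of program plus 36); control incidence *I* of 10%, 15% or 30% over that time, with 30% as an upper case because the control is active; correlation *r* of 0.3 to 0.7 between becoming depressed and SMFQ change; every case confirmed and withdrawn before the visit. The documents give no value for *r* and no time frame for the 30%.

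**The plan's own figure.** Standard error of the difference = 6 × √(2/40) = 1.34. Power at two-sided 5% (assumed) = Φ(4/1.34 − 1.96) = 84.6%, which agrees with the more than 80% in DSMP 7.2.

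**Method.** Weekly hazard h = −ln(1 − I)/44. Fraction lost by week t: control 1 − exp(−ht), MFY 1 − exp(−0.52ht). Remove the top fraction p on a latent depression score correlated r with SMFQ change. The mean of those kept moves by −r × 6 × φ(z)/(1 − p), where z is the normal quantile at 1 − p. Difference seen = 4 + control shift − MFY shift.

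**Worked case** (I = 15%, t = 44, r = 0.5):
- Control: p = 0.150, z = 1.036, φ(z)/(1 − p) = 0.2332/0.850 = 0.274, shift −0.82.
- MFY: p = 1 − 0.85^0.52 = 0.081, z = 1.398, ratio 0.1501/0.919 = 0.163, shift −0.49.
- Difference seen = 4 − 0.82 + 0.49 = 3.67.

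**36 weeks post-program (t = 44), r from 0.3 to 0.7:**

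| Control incidence | Lost, control + MFY | Control too favourable by | MFY too favourable by | True 4 seen as |
|---|---|---|---|---|
| 10% | 4.0 + 2.1 | 0.35–0.82 | 0.21–0.48 | 3.86–3.66 |
| 15% | 6.0 + 3.2 | 0.49–1.15 | 0.29–0.69 | 3.80–3.53 |
| 30% | 12.0 + 6.8 | 0.89–2.09 | 0.55–1.28 | 3.65–3.19 |

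**Other cases:**
- 22 weeks post-program (t = 30): 3.89–3.75 at 10%, 3.85–3.65 at 15%, 3.73–3.38 at 30%.
- Visits timed from program start, as in Table 3: at 15%, W36 loses 7.7 teens and gives 3.83–3.60; W22 loses 4.8 and gives 3.88–3.72.
- Week 8: 1 to 4 teens lost over the three incidences; 3.96–3.77.
- Six-week follow-up always yielding a score (t = 38): 3.82–3.58 at 15%, 3.69–3.27 at 30%.
- Half of cases withdrawn, 30%, t = 44: 9.4 lost; 3.81–3.56.
- Hazard ratio 0.7, 30%, t = 44: 3.79–3.51. At 0.85: 3.90–3.76. At 1: no between-arm bias, but both arms look 0.89–2.09 points too good.
- ANCOVA cutting the residual SD to 4.8 (assumed), 30%, t = 44: 3.72–3.35.

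**The case against.** The strongest reply has four parts.

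*Not every depressed teen is lost.* A teen whose depression is first found at Visit 13 or 16 has an SMFQ there, and the 6-week follow-up could catch others. Section 5.3.3 mentions only referral, and after an SMFQ alert the psychologist judges whether the teen can continue. This stands, so the table is an upper case on withdrawal. A reader might infer that any late SMFQ change excludes all teens who became depressed. The documents support only that it may omit those withdrawn before the visit.

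*The affected analysis may not be run.* No visit is named, and at week 8 little is lost. The random effects model can use scores from before withdrawal. This also stands, provided that complete case is not read as dropping teens with any missed visit; section 9.5 does not say. But section 3 carries the outcome to 36 weeks post-program, and 9.5.2 plots every time point.

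*The bias is small.* At 10 to 15% incidence and 36 weeks post-program, the between-arm shift is 0.14 to 0.47 points, against a standard error of 1.34. The active control could also bring the hazard ratio nearer 1. That is fair for the between-arm contrast. Within-arm change is affected even at a ratio of 1.

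*Some reporting is already planned.* Section 9.6.1 starts with missing-data patterns, 9.6.2 compares drop-out by arm, and the DSMP annual report gives reasons for drop-out. None of these places MDD withdrawals by arm and visit next to the SMFQ results.

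**Conclusion.** The concern holds in a limited form. Followed as written, the plan can make 22- and 36-week complete-case SMFQ change omit teens withdrawn earlier for confirmed MDD.

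- **Within arm:** control improvement is too favourable by about 0.3 to 1.2 points at 10 to 15% incidence, and by up to 2.1 at 30%.
- **Between arms:** a true 4 is seen as about 3.5 to 3.9 at 10 to 15%, and as low as 3.2 at 30%, only if MFY lowers incidence.

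These sizes rest on the assumed incidence, correlation and hazard ratio 0.52. They shrink with Table 3 timing, a ratio nearer 1, or fewer withdrawals.

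A reader might go further and infer a bias favouring MFY, or damage to the time-to-event outcome. Neither follows. If MFY works, the shift is against it, and the time-to-event analysis uses weekly PROMIS scores. Power is not the argument, since 9.6.1 already expects it to be inadequate. This is a point about an exploratory secondary outcome.

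**What to change.** **If collection is open.** State in 9.4.2, 8.3 and DSMP 7.3 that confirmed MDD ends class participation only, with referral for care unchanged. With permission, teen and parent keep receiving the online SMFQ at the remaining scheduled visits, and those scores enter the 9.5.2 and 9.6.1 analyses. Name the visit for the regression, ANCOVA and paired t-test. The cost is an amendment through the independent monitors, NCCIH and then the IRB (DSMP 2), plus a few more online questionnaires.

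**If collection is complete,** as the past tense in 9.5.1 suggests. Make the random effects model the main late-time-point SMFQ analysis, fitted to all available scores including any stopping or 6-week score. Show MDD withdrawals by arm and visit beside any complete-case change. This needs no new data.

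I would not fill missing late scores with the cut-off of 12 in section 7.1. It is a threshold for follow-up by the psychologist, not an outcome value, and a single filled-in score ignores its own uncertainty.

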### 9.4.3: Additional Reasons for Withdrawal of a Participant

Additional reasons a participant may withdraw from the study include:

- The adolescent wishes to withdraw from the study;
- Loss of study eligibility (development of major depression);
- Intervening illness or injury making participation difficult;
- The adolescent develops any condition that, in the opinion of the study psychologist, would make continued participation unsafe.

In the unlikely event that a participant is unable to participate in a group setting, s/he may be withdrawn from the study.

## 9.5: Outcomes

Our primary goal is to develop a depression-prevention program based on mindfulness and self-compassion and to establish the feasibility of its implementation as compared with an active attention-control comparator. Hence, the establishment of quality assurance processes and complete data documentation assume even greater importance than data analysis. Data of multiple types from multiple sources will be captured. For questionnaire assessments, secure internet-based data collection instruments will be used, accessible by internet-capable device.

Quality assurance of these measures will include review of study instruments for range and consistency checks, and descriptive analyses to assess distributions of study variables. Quality assurance of qualitative measures include 1) maintaining a spreadsheet to log scheduled, completed, transcribed, and analyzed focus groups and interviews; 2) establishing a transcription template to ensure data is uniform in appearance; 3) arranging for secure storage of recordings and transcripts on REDCap; 4) review of consistency of styles across interviewers; and 5) review of recordings to assess accuracy of transcriptions.

All statistical analyses will utilize all adolescents who were randomized to one of the intervention arms and who attended at least one class. Individuals who were unable to attend a class are excluded. Complete case analyses are planned (without imputations).

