### Design and Outcomes

Four cohorts of adolescents, each with 20 participants, will be recruited. In each cohort, twenty individuals will be randomized with 10 each in the mindful self-compassion group (Making Friends with Yourself) and the healthy behavior skills group. In addition, each adolescent will be accompanied by a parent (n=80). Adolescents complete brief weekly questionnaires to assess depressive symptoms as well as a longer set of online questionnaires at baseline, weeks 4 and 8 of the intervention, and 3 and 36 weeks post-intervention. Parents complete a questionnaire at baseline, 3 and 36 weeks post-intervention.

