Randomization will be stratified by gender. As soon as 20 eligible adolescents qualify for enrollment, they will be allocated to either the MFY or healthy lifestyle groups, using a specially-designed computer program which utilizes a random number generator with a permuted block design to ensure that the

number of subjects allocated to the two arms over time are equal and to conceal the allocation. This will continue through 4 cohorts of adolescents (n=80). During participation, adolescents will keep a daily online diary, accessible from a cell phone, to document homework practice. Their engagement in the program will be captured by audiotaping program sessions. After each program's completion,

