#### 4.3.4: Randomization

Although the study is not designed as an RCT, we do plan to test our randomization system. In all but the first two cohorts, as soon as 14-20 eligible adolescents qualify for enrollment, they will be allocated to one of the educational groups, using a specially-designed computer program (in REDCap). This program requires the operator to check off inclusion/exclusion criterion for each subject and confirm that subjects have been consented. The program utilizes a random-numbers generator with a permuted block design (blocks of 2 to 4) to ensure that the numbers of subjects allocated to the two arms over time are equal and to conceal the allocation. Randomization is stratified by gender.

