#### Randomization

After the first two groups (one each of MFY and HLG), randomization occurs one week before the first class. A designated study team member will use the randomization feature of REDCap to randomize participants. The procedure involves a review of eligibility followed by an assignment to one of the groups.

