## 9.3: Definition of Populations

The ITT (Intent to treat) population is any participant randomized to an intervention group, whether or not he/she participates. “Per protocol” populations (“Completers”) are participants who do not formally withdraw.

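### Section 9.5 bases all analyses on randomised teens who came to at least one class, so the ITT set defined in 9.3 is never used and the exploratory between-arm estimates carry an avoidable post-randomisation exclusion

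*Combined protocol and SAP*

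**What the plan says.** Section 9.3 (Definition of Populations) defines two sets. The first is inclusive: "The ITT (Intent to treat) population is any participant randomized to an intervention group, whether or not he/she participates". The second, per protocol or completers, "are participants who do not formally withdraw".

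Section 9.5 (Outcomes) uses neither: "All statistical analyses will utilize all adolescents who were randomized to one of the intervention arms and who attended at least one class". It adds: "Individuals who were unable to attend a class are excluded". It also plans complete-case analysis without imputation.

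The rule in 9.5 stands above the Kaplan-Meier and Cox analyses of 9.5.1 and the ANCOVA and random effects models of 9.5.2. ITT is not mentioned again in 9.5, 9.6 or the Data Safety Monitoring Plan.

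On timing, the Randomization paragraph of 6.2.2 says "After the first two groups (one each of MFY and HLG), randomization occurs one week before the first class". Under Visit 2 in 6.2.3, families complete the baseline questionnaires and are then told their assignment with the time and place.

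**The concern.** A teen who misses class 1 but comes later stays in the analysis. Only teens who attend no class are removed. Whether a teen falls in that group is settled after allocation, and after the family knows when and where the assigned programme meets. What remains is therefore not guaranteed to be the two groups as randomised.

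Bias in the arm comparison needs two things together: the rate or type of zero-class teen differs by arm, and those teens' risk of the outcome differs from the rest.

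The estimates are exploratory (9.1, 9.6.1), but Purpose 3 in section 1.2 says they are to inform the planning of a powered trial. For that use they should come from the set that compares the arms as randomised, which the protocol already defines.

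**Working it through.** **Comparing the sets**

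| Set | Where | Zero-class teen | Analysis assigned |
|---|---|---|---|
| ITT | 9.3 | In | None |
| Per protocol (completers) | 9.3 | In, unless formally withdrawn | None |
| Randomised and came to one or more classes | 9.5 only | Out | All statistical analyses |

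This mismatch is established by the text alone. The plan gives no zero-class rate and no figure for its effect, so there is nothing to reproduce. What follows is an illustration on assumed inputs.

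**Inputs**
- Risk as randomised: 30% in both arms, i.e. no true effect. Section 9.2.1 expects more than 30% in untreated teens; using 30% in both arms is an assumption.
- z, the zero-class share of an arm: assumed 5% to 20%.
- r, the risk among zero-class teens: assumed 30% to 60%.
- 40 per arm, from the stated total of 80.

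**Formulas**
- Risk left after exclusion: p = (0.30 − z·r)/(1 − z).
- Apparent hazard ratio (HR), MFY against control: ln(1 − p_MFY)/ln(1 − p_control), a proportional hazards approximation.
- SE(log HR) = √(1/d₁ + 1/d₂), where d₁ and d₂ are the events per arm.

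**Zero-class teens in the MFY arm only** (control risk stays 0.30)

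| z | r | p | Apparent HR |
|---|---|---|---|
| 10% | 30% | 0.300 | 1.00 |
| 10% | 40% | 0.289 | 0.96 |
| 10% | 50% | 0.278 | 0.91 |
| 20% | 30% | 0.300 | 1.00 |
| 20% | 40% | 0.275 | 0.90 |
| 20% | 50% | 0.250 | 0.81 |

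The last row is ln(0.75)/ln(0.70) = 0.807.

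**Zero-class teens in both arms**
- Equal share and equal risk: HR 1.00.
- 15% MFY against 5% control: HR 0.90 at r = 50%, 0.85 at r = 60%.
- 20% against 5%: HR 0.84 at r = 50%, 0.76 at r = 60%.
- Equal shares of 10%, but r = 50% in MFY and 30% in control: p = 0.278 against 0.300, HR 0.91. A difference in type is enough without a difference in rate.

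**Direction.** The sign follows from the assumptions. If the same teens are lost from the control arm instead, 0.807 becomes 1/0.807 = 1.24. If zero-class teens in MFY are at lower risk, say r = 10% with z = 20%, then p = (0.30 − 0.02)/0.80 = 0.35 and HR = ln(0.65)/ln(0.70) = 1.21.

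**Against sampling error, 40 per arm**
- HR 0.807: events are 40 × 0.30 = 12 and 32 × 0.25 = 8. SE = √(1/12 + 1/8) = 0.456. The shift is |ln 0.807| = 0.215, or 0.47 SE. A 95% interval around 0.807 would run from 0.33 to 1.97.
- HR 0.76 (20% against 5%, r = 60%): events are 32 × 0.225 = 7.2 and 38 × 0.284 = 10.8. SE = √(1/7.2 + 1/10.8) = 0.481. The shift is 0.271, or 0.56 SE.

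**What ITT recovers** (z = 20%, r = 50%: 8 zero-class teens, 4 with the event)
- None report follow-up: 8/32 = 0.25, HR 0.81, the same as under 9.5.
- Half report: 10/36 = 0.278, HR 0.91.
- All report: 12/40 = 0.30, HR 1.00.

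**The case against.** The best case for the plan has four parts.

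1. **Masking.** Section 5.2.1 withholds programme names and presents both programmes as beneficial. Before class 1 a teen has little reason to stay away from one arm rather than the other, beyond time and place. This stands. It lowers the chance of differential non-attendance, but does not remove it or resolve 9.3 against 9.5.

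2. **ITT may add no data.** A reader might infer that outcome data do not depend on attendance, because PROMIS goes out weekly through REDCap (9.4.2) and questionnaires by link (10.3.3). The documents do not support that as a general statement. Section 5.1.3 ties PROMIS to teens who are in the 8-week course, Appendix B.e labels it as a measure for participants during the intervention, and 8.3 limits follow-up after discontinuation to 6 weeks and by permission. A zero-class teen with no post-baseline PROMIS contributes nothing to a Cox model. This stands as a limit on the remedy.

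3. **Feasibility counts.** A reader might infer that 9.5 also strips zero-class teens from the completion and drop-out counts in 9.6.2. Read literally, it could. But those counts read naturally as covering everyone enrolled, and non-completers are to be telephoned. The sensible reading is that they are in; one sentence would settle it.

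4. **Exploratory status.** Section 9.1 disclaims hypotheses, 9.6.1 disclaims power, and the 9.5 rule is openly stated. This limits the severity. It is not a reason to leave the defined ITT set unused.

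**Conclusion.** The point holds in a limited form. That 9.5 replaces the 9.3 ITT set with an unnamed one, and that no analysis uses ITT, is certain from the text. That the exclusion can bias the between-arm estimates follows from its timing. That it does so is not shown: the documents give neither a zero-class rate nor those teens' risk.

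A reader might infer a bias in favour of MFY. Nothing in the documents fixes the direction; the same assumptions with the arms exchanged give the reciprocal hazard ratio. In the cases set against sampling error, the shift was 0.47 to 0.56 standard errors at 40 per arm, so it is probably well under one standard error. Those figures rest on the assumed 30% risk, the assumed zero-class shares and risks, and proportional hazards.

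This is a cheap correction to the validity of the analysis set, not a demonstrated large error. The complete-case rule is not at issue here. The protocol's differing statements about which cohorts were randomised are a separate matter and should be raised separately.

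**What to change.** - **9.5:** make the 9.3 ITT set, analysed as randomised, the main set for between-arm analyses, including every randomised teen with outcome data. The no-imputation rule can stay.
- **9.3 and 9.5:** name the set of randomised teens who came to one or more classes as a modified ITT set, and keep it as a sensitivity analysis.
- **Reporting:** by arm, give the number of zero-class teens, their baseline SMFQ (scheduled for completion before assignment is disclosed) and their missing follow-up.
- **9.6.2:** state that the comparison of drop-out by arm counts zero-class teens.

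The cost is wording in three sections and one small table, with no new data collection. The drawback is that zero-class teens may have little or no post-baseline data. ITT may then reduce the bias only partly or not at all, and including teens who received no programme may slightly dilute the estimates. The by-arm table would still let a reader judge how much the exclusion could matter.
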